Participants (N=110: n=10 for the pilot study, n=100 for the feasibility trial): Inclusion criteria: (a) at least 18 years of age; (b) daily smokers (≥ 5 CPD); (c) for at least 2 years; (d) own an Android phone or iPhone; (f) fluent in English as content is only available in English*; and (g) motivated to quit smoking, as indicated by ≥ 18 of 20 on the Action subscale of the Readiness to Change Questionnaire [78] as previously [4, 5]. Exclusion criteria: (a) e-cigarette use (some days/every day) because the smartband technology is not yet able to distinguish e-cigarette use. Recent reports indicate that 10.6% of current cigarette smokers had used e-cigarettes in the past 30 days and 3.6% regularly use e-cigarettes (≥ 20 of the past 30-days) [79]. Therefore, we do not expect dual use to negatively impact recruitment. Other tobacco product use including e-cigarettes will be monitored at each time point (see "Assessments"). No other exclusion criteria. Possible confounds include concurrent use of quit smoking and other psychotropic medications. These will be monitored for confounding effects using our medication use questionnaire.

*Materials will be developed in Spanish during the course of this research, however only English-speaking individuals will be currently enrolled.

7. **Subject classification:** Check off all classifications of subjects that will be specifically recruited for enrollment in the research project. Will subjects who may require additional safeguards or other considerations be enrolled in the study? If so, identify the population of subjects requiring special safeguards and provide a justification for their involvement.

 Children	 Healthy	 Fetal material, placenta, or dead fetus
 Non-English Speaking	 Prisoners	 Economically disadvantaged persons
 Decisionally Impaired	 Employees	 Pregnant women and/or fetuses
 Yale Students	 Females of childbearing potential	

NOTE: Is this research proposal designed to enroll children who are wards of the state as potential subjects?

Yes No

8. **Inclusion/Exclusion Criteria:** What are the criteria used to determine subject inclusion or exclusion?

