Secondary data analysis: As a secondary aim, we will evaluate change in smoking (cigarettes per day) and abstinence at the end-of-study survey. Abstinence will be measured by: 1) self-reported one week point prevalence abstinence and continuous abstinence (> 5 cigarettes since quit date), 2) automatic smartband smoking monitoring and detection for 7 days prior to the assessment, and, 3) a random subset of individuals (50%) who report one-week point-prevalence abstinence at end-of-study will be shipped carbon monoxide breath monitors (coVita, LLC), or saliva kits (Alere iScreen OFD Cotinine Saliva Test) to confirm abstinence from smoking (<10 ppm or negative saliva test) via video chat with a researcher as previously [4, 5] or by submitting a recorded video via email or text. Abstinence rates will be reported for each measure. These data will be used to provide preliminary evidence about whether smartband-based smoking monitoring can inform measures of abstinence. We will use descriptive statistics to inform future studies. Additionally, all interactions with the app will be automatically tracked and evaluated related to engagement and secondary outcomes.

Missing data: In our recent trial [4, 5], most individuals dropped out upon enrollment. Treatment starters used the app 17 ± 8 out of 22 days and completed ratings (EMA) on 14 ± 9 days. We then had 53% treatment completers –defined as 60% of treatment. Retention to the primary 6mo. survey was 84% despite whether subjects had engaged with treatment. Therefore, we do not anticipate significant missing survey data. We are unable to estimate retention at each step but will measure this. Relevant to our aims, other missing data may include smoking data from not wearing the smartband, or ratings data. Primary analyses will use missing at random (MAR) assumptions but we will also perform sensitivity analyses under reasonable missing not at random (MNAR) [80, 81]. For singly-measured outcomes we will use multiple imputation [82, 83] under MAR (primary) and MNAR (secondary analyses). For longitudinal outcomes, our primary approach will be full-information maximum likelihood under MAR [84]. We will fit pattern mixture longitudinal models to test the effect of deviations from MAR [85]. We will compare retained vs. dropouts on different characteristics to inform the MNAR models.

SECTION II: RESEARCH INVOLVING DRUGS, BIOLOGICS, RADIOTRACERS, PLACEBOS AND DEVICES

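### Separate abstinence rates cannot show whether the smartband and self-report classify the same people as abstinent; a paired table should be prespecified

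*Combined protocol and SAP*

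**What the plan says.** The text is in section 13, Statistical Considerations, under Secondary data analysis. Three measures are taken at the end of the study:

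- self-reported seven-day point prevalence and continuous abstinence;
- "automatic smartband smoking monitoring and detection for 7 days prior to the assessment";
- a CO breath test or saliva cotinine test, sent to "a random subset of individuals (50%) who report one-week point-prevalence abstinence at end-of-study".

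The stated output is that "Abstinence rates will be reported for each measure". The next sentence gives the use: "These data will be used to provide preliminary evidence about whether smartband-based smoking monitoring can inform measures of abstinence". The only method named is in the sentence after that: "We will use descriptive statistics to inform future studies". No cross-tabulation, percent agreement, kappa or predictive value is specified for abstinence anywhere in the document.

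The Missing data paragraph recognises that smoking data will be lost when the band is not worn. No rule says how much wear is needed before a participant counts as abstinent by the band.

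**The concern.** Whether the band can inform an abstinence measure depends on whether it sorts the same individuals the same way as the other measures. Two measures can give identical rates while calling different people abstinent, so rates reported side by side could look reassuring when the band adds noise, or be uninformative when it works well. The larger trial that this study is meant to inform would then lack the evidence it needs on this question, although the paired data would be in hand.

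The accuracy check under Aim 1 does not fill the gap. It counts detected episodes and false alarms in the first 21 days, before the quit date, and its reference is the participant's own confirmation, denial or report of a missed cigarette. It says nothing about person-level abstinence at day 60.

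**Working it through.** The plan gives no precision or agreement figure for this analysis, so there is none to reproduce.

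**Inputs.** The feasibility trial has 100 participants ("n=10 for the pilot study, n=100 for the feasibility trial", section 6). Abstinence rates for illustration come from prior trials cited in the background: 13% (section A.1), and 36% post-treatment and 31% at follow-up (section A.3). Numbers analysed are 100, or 84 and 53 if the prior trial's 84% survey retention or 53% treatment completion applied (section 13, Missing data). All of these are assumptions for the present trial.

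**Step 1: what equal rates allow.** Let n people have both measures, a be abstinent by self-report, b by the band, and x by both. Then

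- agreement Po = (n − a − b + 2x)/n, where x can run from max(0, a + b − n) to min(a, b);
- chance agreement Pe = [ab + (n − a)(n − b)]/n²;
- kappa = (Po − Pe)/(1 − Pe).

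The two rates fix a and b but leave x free. With n = 100:

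| Both rates | Lowest Po (x = 0) | Highest Po | Pe | Kappa range |
|---|---|---|---|---|
| 13% | (100 − 26)/100 = 74% | 100% | 77% | −0.15 to 1.00 |
| 31% | (100 − 62)/100 = 38% | 100% | 57% | −0.45 to 1.00 |
| 36% | (100 − 72)/100 = 28% | 100% | 54% | −0.56 to 1.00 |

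In every row, the share of self-reported abstainers whom the band also calls abstinent can be anything from 0% to 100%. At n = 84 and n = 53 the lowest agreement is almost the same (74% and 74%; 38% and 40%; 29% and 28%).

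**Step 2: unequal rates.** With 36% and 31% at n = 100, agreement lies between 33% and 95%, and kappa between −0.50 and 0.89. A difference in rates proves some disagreement, but not how much or in whom.

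**Step 3: what a paired table would give.** Exact 95% intervals for observed agreement near 90%:

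- 90/100: 82.4% to 95.1%;
- 76/84: 82.1% to 95.8%;
- 48/53: 79.3% to 96.9%.

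**Step 4: the tested subset.** Half of 13 to 36 self-reported abstainers is about 6 to 18 people at n = 100. If all test negative, the exact 95% lower limit is 0.025^(1/6) = 54% with 6 tested and 0.025^(1/18) = 81% with 18 tested. Everyone tested reports abstinence. If q is the proportion testing negative, observed agreement between self-report and test is q, and chance agreement is 1 × q + 0 × (1 − q) = q. Kappa is therefore (q − q)/(1 − q) = 0, or undefined when q = 1. The proportion confirmed is the right summary.

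**Step 5: a verified rate.** Use the self-reported rate times the confirmation rate among those tested. With 36% self-reported and 16 of 18 confirmed, this is 36% × 16/18 = 32%. Doubling the confirmed count gives the same answer only if every selected person returns a test.

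**The case against.** The strongest reply is that the plan is unspecific rather than wrong. It says that the data, not just the rates, will be used, and a 2x2 table is a descriptive statistic. That stands: a reader might infer that the plan confines itself to comparing rates, and the text does not go that far. But rates are the only output it names, and one sentence would settle the matter.

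A reader might also infer that measuring agreement is the declared reason for collecting all three measures. It is not. Abstinence is a secondary outcome in its own right, the biochemical test is there to confirm it, and the document speaks of the band informing abstinence measures, not of replacing them.

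Nor is self-report against biochemistry unpaired. Testing is nested in self-reported abstainers, so the confirmation rate is already a person-level result. The gap is the band against the other two.

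It is tempting to say that the verified rate will come out at about half its true value because only half are tested. The document never says that the confirmed count will be divided by all participants, so this is a risk of leaving the denominator unstated, not a planned error.

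Finally, the lowest agreement figures need complete non-overlap, which is implausible. They show what the rates leave open, not what to expect.

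**Conclusion.** The point holds as an inexpensive improvement to a secondary, descriptive analysis. No feasibility criterion depends on it. Rates alone leave person-level agreement between band and self-report open over 74% to 100% at 13% abstinent and 28% to 100% at 36%, assuming equal rates and abstinence levels like those of the cited prior trials. A paired table would instead give an interval of about 13 percentage points at n = 100, or about 18 at n = 53, if agreement were near 90%.

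Two limits remain whatever is tabulated. Because no self-reported smoker is tested, whole-sample sensitivity and specificity against biochemistry cannot be estimated. And kits are shipped after the end-of-study report, so the test falls after the seven-day window of the band and self-report. A reader might think that asking smoking status again on the test day would align the three. It would not move the band's window, and the document gives no detection window for either test.

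**What to change.** Add to section 13, Secondary data analysis:

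1. A 2x2 table of band-defined against self-reported seven-day abstinence at the end of the study, among participants with both measures. Report the four counts, percent agreement and kappa, with 95% intervals (exact for proportions). Count someone as band-abstinent only if the band was worn enough in those seven days; the 12 hours per day already used for payment in section D.10 is one candidate. Otherwise treat band status as missing, and report how many are missing.
2. In the tested subset, the proportion confirmed and a band-by-test-result count table, with exact intervals and no kappa. State that the subset is small (about 6 to 18 at n = 100) and that whole-sample sensitivity and specificity cannot be estimated.
3. If a trial-level verified rate is quoted, compute it as the self-reported rate times the confirmation rate among those actually tested, and report tests not returned.
4. A stated limitation that the test is done after the band and self-report window.

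Separately, the continuous-abstinence threshold is written with a greater-than sign in this paragraph and a less-than sign in section D.4 and the section 13 Overview. These should be reconciled before any continuous-abstinence rate is tabulated.

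The cost is two small tables, a wear rule and a few sentences. No new data collection is needed.

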If this section (or one of its parts, A or B) is not applicable, check off N/A and delete the rest of the section.

A. RADIOTRACERS N/A

B. DRUGS/BIOLOGICS N/A

C. DEVICES N/A

SECTION III: RECRUITMENT/CONSENT AND ASSENT PROCEDURES**1. Targeted Enrollment: Give the number of subjects:**

- a. Targeted for enrollment at Yale for this protocol: N=110 but we will enroll N=150 to account for estimated high attrition as in our previous randomized clinical trial of a smartphone app for smoking cessation and other similar trials.
- b. If this is a multi-site study, give the total number of subjects targeted across all sites: *Write here*

2. Indicate recruitment methods below. Attach copies of any recruitment materials that will be used.

 Flyers	 Internet/web postings	 Radio
 Posters	 Mass email solicitation	 Telephone
 Letter	 Departmental/Center website	 Television
 Medical record review*	 Departmental/Center research boards	 Newspaper
 Departmental/Center newsletters	 Web-based clinical trial registries	 Clinicaltrials.gov
 YCCI Recruitment database	 Social Media (Twitter/Facebook):	
 Other:		

Google, Facebook, Reddit ads

* Requests for medical records should be made through JDAT as described at
<http://medicine.yale.edu/ycci/oncore/availableservices/datarequests/datarequests.aspx>

3. Recruitment Procedures:

- a. Describe how potential subjects will be identified. *Write here*
- b. Describe how potential subjects are contacted. *Write here*
- c. Who is recruiting potential subjects? *Write here*

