2. **Payments for Participation (Economic Considerations):** Describe any payments that will be made to subjects, the amount and schedule of payments, and the conditions for receiving this compensation. Study compensation will be: \$10 upon completion of the zoom/online training, \$20 upon completion of the second study survey, and \$10 upon completion of the third study survey. At the end of the study, they will be paid \$1 per day for each day of the 60-day study that they have worn their smartband for 12 waking hours (up to \$60). At the end of the study, they will also be paid \$10 for the end of study survey, and a \$50 bonus payment if they have completed all parts of the study. **Total study payment will be up to \$160** (up to \$40 paid upon each survey completion, up to \$120 paid at the end of the study). Please note that all study equipment (smartband, CO-monitor, saliva kit if applicable) must be returned before the final study payment. Finally, they may be invited to take part in an optional debriefing at the end of the study, for which they will be paid an additional \$10. Study payments will be by amazon.com gift card.
3. **Costs for Participation (Economic Considerations):** Clearly describe the subject's costs associated with participation in the research, and the interventions or procedures of the study that will be provided at no cost to subjects. To participate in the study, participants will be required to already own a smartphone.
4. **In Case of Injury:** This section is required for any research involving more than minimal risk, and for minimal risk research that presents the potential for physical harm (e.g., research involving blood draws).
 - a. Will medical treatment be available if research-related injury occurs? *Write here*
 - b. Where and from whom may treatment be obtained? *Write here*
 - c. Are there any limits to the treatment being provided? *Write here*
 - d. Who will pay for this treatment? *Write here*
 - e. How will the medical treatment be accessed by subjects? *Write here*

This protocol is deemed to be of minimal risk. If subjects develop a mental or physical problem as a result of involvement in this study, they will seek their own treatment independently from the study. The subject's insurance carrier will be expected to pay the costs of such treatment. No financial compensation is available for this treatment.

IMPORTANT REMINDERS

Will this study have a billable service? Yes No

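### No rule for CO or saliva tests that are sent but never submitted: under the default MAR rule, or if only submitted tests are analysed, the confirmed abstinence rate is likely to be too high

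*Combined protocol and SAP*

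**What the plan says.** Section 13, Secondary data analysis, sets the outcome: "As a secondary aim, we will evaluate change in smoking (cigarettes per day) and abstinence at the end-of-study survey". Abstinence is measured by self-report, by the smartband over the preceding seven days, and by a biochemical test. For the test, a random 50% of those who report one-week abstinence at the end of the study are shipped a CO monitor or saliva kit "to confirm abstinence from smoking (<10 ppm or negative saliva test) via video chat with a researcher", or they may send a recorded video. A rate is to be reported for each measure, with descriptive statistics, to inform later studies and to show whether the smartband can contribute to measuring abstinence.

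The Missing data paragraph of the same section gives the general rule: "Primary analyses will use missing at random (MAR) assumptions but we will also perform sensitivity analyses under reasonable missing not at random (MNAR". It then splits by type of outcome. For outcomes measured once: "For singly-measured outcomes we will use multiple imputation [82, 83] under MAR (primary) and MNAR (secondary analyses". For repeated outcomes: "For longitudinal outcomes, our primary approach will be full-information maximum likelihood under MAR [84", with pattern-mixture models to examine departures from MAR. The paragraph names survey, smartband and ratings data as possibly missing. It does not mention the CO or saliva test.

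No part of the document says how a sent but unsubmitted test is counted, what the denominator of the confirmed rate is, or which MNAR scenario applies to missing abstinence status.

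**The concern.** Two groups of self-reported abstainers have no test result. The half not selected are missing by random design, and MAR is true for them. Those who were sent a kit and submit nothing have selected themselves. The test is there to check self-report, and Background A.2 itself notes that smokers under-report or deny smoking. A person who reported abstinence but has smoked has a direct reason not to be tested on camera. The plan does not separate the two groups.

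If the missing results are imputed under MAR, the self-selected group receives the confirmation rate of submitters, or of similar submitters. If only submitted tests are analysed, the group leaves the denominator. Either way an untaken test does not lower the confirmed rate. That rate is the check on self-report and a reference for the smartband measure, so inflating it makes both uses less reliable.

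A related but smaller issue concerns self-reported abstinence. The primary estimate is under MAR, and the planned MNAR analyses have no stated scenario, so a reader will not know how far the rate depends on non-responders.

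**Working it through.** The plan states no expected abstinence rate, test submission rate or confirmation rate, so there is no figure of its own to reproduce. The quantities below are assumptions unless a source is given.

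**1. Which rule applies.** The test is taken once, at the end of the study, so the rule for singly-measured outcomes covers it by default. Smoking status is collected at baseline and days 21, 30 and 60 (Table 1), so self-reported abstinence may fall under the longitudinal rule instead. Both rules are MAR.

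**2. Overstatement of the confirmed share.** Let q be the share of sent tests submitted, c the share of submitted tests that confirm abstinence, and a the share of non-submitters who are truly abstinent.

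- MAR without predictors, or submitted tests only: c
- True share among those selected: qc + (1 − q)a
- Ratio: c / [qc + (1 − q)a]. With a = 0 this is 1/q. With a = c/2 it is 2/(1 + q). With a = c there is no bias.

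| q (assumed) | Overstatement, a = 0 | Overstatement, a = c/2 |
|---|---|---|
| 90% | 1/0.90 − 1 = 11% | 2/1.90 − 1 = 5% |
| 70% | 1/0.70 − 1 = 43% | 2/1.70 − 1 = 18% |
| 50% | 1/0.50 − 1 = 100% | 2/1.50 − 1 = 33% |

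**3. On the scale of the reported rate.** Take 31% self-reported abstinence (the 17-week figure for mindfulness training in the earlier in-person trial, Background A.3) and an assumed c of 90%. MAR without predictors, or submitted tests only, gives 0.31 × 0.90 = 27.9%. Counting unsubmitted tests as not confirmed gives 0.31 × 0.90 × q = 25.1%, 19.5% and 14.0% for q of 90%, 70% and 50%.

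**4. Number of kits.** With 100 participants in the feasibility trial (Subject Population) and 31% reporting abstinence, 100 × 0.31 × 0.50 = 15.5, so 15 or 16 kits are sent. Each unreturned kit moves the confirmed share by up to 1/15.5, about 6 percentage points.

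**5. Self-reported abstinence.** Let p be the responders' rate and r the response rate. MAR without predictors gives p; counting missing as smoking gives p × r. With p = 31% and r = 84% (six-month survey retention in the earlier app trial, section 13), the figures are 31% and 0.31 × 0.84 = 26.0%.

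Predictors narrow this gap. Suppose that 53% of participants engage, with 36% abstinent and 95% responding, and that 47% do not, with 5% abstinent and 71.6% responding. Overall response is 84%.

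- Responders' rate: (0.53 × 0.95 × 0.36 + 0.47 × 0.716 × 0.05) / 0.84 = 0.198 / 0.84 = 23.6%
- Rate that a correct MAR model gives non-responders: (0.53 × 0.05 × 0.36 + 0.47 × 0.284 × 0.05) / 0.16 = 10.1%
- Overall MAR estimate: 0.53 × 0.36 + 0.47 × 0.05 = 21.4%
- Missing counted as smoking: 19.8%

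The gap is 1.6 points.

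**The case against.** The strongest objection is that the plan never says an unsubmitted test will be imputed. It promises descriptive rates per measure, so a reader who infers that MAR imputation of the test is planned goes beyond the text. This stands. It does not remove the problem, because reporting submitted tests only biases the rate in the same direction.

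A reader might also infer that all non-responders are credited with the responders' quit rate. That is exact only if the imputation model has no predictors. The model is not specified, and day-21 and day-30 status, engagement and smartband data are all available. The example above shows how much they can matter. MNAR analyses are also already planned, so for self-report what is missing is a named scenario shown beside the MAR figure. Making missing-as-smoking the primary rule would be a debatable choice, since some non-responders are abstinent.

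Two further readings are not supported:

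- Section 13 says "Therefore, we do not anticipate significant missing survey data", while Section III, Targeted Enrollment, says "we will enroll N=150 to account for estimated high attrition as in our previous randomized clinical trial". This looks like a contradiction, but section 13 separates early dropout from survey retention, and over-enrolling for the first is compatible with good response to the second. Nor do 110/150 = 73%, or the 53% treatment completion in the earlier trial, describe test submission. Only people who have just completed the final survey and reported abstinence are sent a test.
- Section VI, Payments, has no item for the test and requires only that "all study equipment (smartband, CO-monitor, saliva kit if applicable) must be returned before the final study payment". It would be wrong to conclude that there is no incentive: the $50 completion bonus may be meant to cover the test.

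Finally, the stakes are limited. The trial has one arm, and abstinence is a descriptive secondary outcome without a threshold. At a high submission rate only a few results would be missing.

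**Conclusion.** The point holds in this form: the plan has no rule or denominator for tests sent but not submitted, and either available reading treats self-selected non-submitters like submitters. Upward bias in the confirmed rate is likely but not certain. It requires non-submitters to be abstinent less often than submitters are confirmed.

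In the limiting case the overstatement is 11% to 100% for submission rates from 90% to 50%. It falls to 5% to 33% if non-submitters are abstinent half as often as submitters are confirmed. These submission rates are assumed, because the documents give none. For self-reported abstinence the remaining point is one of presentation: name the MNAR bound and show it.

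This is a cheap improvement to a secondary outcome. It does not affect the feasibility aims or any between-group comparison.

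**What to change.** In section 13:

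(a) **Biochemical confirmation.** Use as denominator the self-reported abstainers randomly selected for testing. Count a selected person with no submitted result as not confirmed. Extrapolate only to the randomly unselected half: overall confirmed rate = self-reported rate × (confirmed / selected). Report the numbers selected, submitted and confirmed. State which self-reported rate enters the product. A MAR-based rate would also extend confirmation to survey non-responders, whereas the bound in (b) would not.

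(b) **Self-reported abstinence.** Keep the MAR estimate, state whether it comes from FIML or multiple imputation, and list the predictors: day-21 and day-30 status, engagement and smartband data. Beside it report, as a named MNAR bound, the rate with all enrolled participants as denominator and missing counted as smoking.

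The cost is a few sentences and a few lines of code, with no new data. The reported rates will be less favourable. The confirmed rate in (a) and the bound in (b) are both conservative, because some people with no result are truly abstinent, and the report should say so.
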